Participating Medical Centers:	1. University of Alabama at Birmingham (UAB) 2. Temple University Medical Center 3. University of Michigan Medical Center 4. University of Minnesota 5. Tulane University	

Data Coordinating Center:	[name]., [name]. Division of Preventive Medicine Dept. of Medicine UAB
Sponsors:	UAB
Study Rationale:	On the basis of substantial preliminary data, we hypothesize that reactive oxygen species (ROS) generated by nicotinamide adenine dinucleotide phosphate (NADPH) oxidase (NOX) enzymes play an important role in the development of idiopathic pulmonary fibrosis (IPF). In particular, GKT137831 has shown marked efficacy in preclinical models of IPF, including the prevention of myofibroblast activation, regression of fibrosis, and improved survival. GKT137831 is an orally available small molecule inhibitor of NOX 1 and 4, which has shown therapeutic efficacy and good safety and tolerability in patients with fibrotic liver disease. We hope that treatment with GKT137831 could result in significant benefit for a lung disease that has, until now, been almost invariably inexorable. This clinical trial has the potential to profoundly affect current paradigms and treatment approaches to patients with IPF.
Study Objectives:	The primary goal of this multicenter, randomized, double-blind, Phase II clinical trial is to determine effects of GKT137831 on plasma levels of o,o' -dityrosine, a mechanistic biomarker of oxidative stress, in comparison to effects of placebo alone. Drug effects on validated clinical endpoints will be also assessed, including forced vital capacity (FVC) and six-minute walk distance (6MWD). We anticipate the findings of this study will lead to larger incremental trial(s) to definitively establish the clinical efficacy and favorable safety profile of this treatment.
Study Hypothesis:	Our central hypothesis is that treatment with the NOX1/4 inhibitor GKT137831 will reduce oxidative injury in IPF patients
Study Aims:	
 1. To conduct a proof-of-concept, mechanistically-driven, double-blinded, placebo-controlled trial, to examine effects of GKT137831 administration on a surrogate measure of oxidative stress and pulmonary injury in IPF patients. 2. To determine effects of GKT137831 administration in IPF patients, compared to placebo, on four secondary efficacy endpoints: (a) levels of collagen degradation product, C1M, measured in sera by ELISA; (b) and forced vital capacity (FVC) at baseline and 24 weeks. Also (c) six-minute walk distances (6MWD) will be measured at baseline and 24 weeks; and (d) adverse events (AE) will be recorded throughout the subject's participation in this study.

Study Design:	
Following screening assessments, IPF patients who meet all inclusion/exclusion criteria will be randomly assigned to receive one of the following treatments in a ratio of 1:1:
 
 • Arm A (n=30) – GKT137831 Treatment: GKT137831 will be administered orally, at a dose of 400 mg bid, for a total of 24 weeks. • Arm B (n=30) - Placebo Treatment: Arm B subjects will receive matching placebo for the same duration. 
Participants will be followed in face-to-face visits with trial personnel every 6 weeks for 24 weeks to assess drug effects and monitor safety during their treatments, and by phone surveillances one month thereafter.

Planned Sample Size:	A total of 60 subjects will be enrolled in this multi-center trial from among IPF patients at 5 participating medical centers.
Duration of Study:	Up to a maximum of 32 weeks, including screening (4 weeks maximum), drug administration for 24 weeks, and then a final surveillance phone contact 4 weeks later.
Inclusion Criteria:	
 1) Age between 40-85 years old. 2) A diagnosis of IPF that fulfills current ATS/ERS Consensus Criteria (1). 3) IPF duration <10 years, based on the date of definitive diagnosis. 4) Ability and willingness to give informed consent and adhere to study requirements. 5) Ratio of forced expiratory volume in 1 second to forced vital capacity (FEV₁/FVC) >70% of predicted values
Major Exclusion Criteria:	
 1) Diagnosis of major comorbidities expected to interfere with study participation 2) History of malignancy within the last 5 years, excluding basal or squamous cell skin cancer and low-risk prostate cancer, the latter defined as stage T1 or T2a, with prostate specific antigen <10 ng/dl. NOX inhibition is not known to promote cancer, and these criteria are within current guidelines. 3) The occurrence of any acute infection requiring systemic antibiotic therapy within 2 weeks prior to Screening (Visit 1).

	
 4) Treatment for >14 days within the preceding month with >20 mg. prednisone (or equivalent) or any treatment during the last month with a cellular immunosuppressant (e.g., cyclophosphamide, methotrexate, calcineurin inhibitors, etc.), given increased risks of opportunistic infections. 5) Treatment with any investigational agent within 4 weeks of Screening (Visit 1) or 5 half-lives of the investigational medicinal product (whichever is longer). 6) Fertile women who do not agree to abstinence or an effective form of contraception (as approved by the investigator), or who are breast feeding, for 4 weeks before randomization until 90 days after the last administration of study medication (or placebo). 7) Men who are not surgically sterile and do not agree to remain abstinent from heterosexual intercourse or use effective contraception (as approved by the investigator), and refrain from donating sperm, from the time of giving informed consent until 90 days after the last administration of study medication (or placebo). 8) Subjects with known hypersensitivity to GKT137831 or its excipients (e.g. capsule "bulking" agents). 9) A history of bone marrow disorder including aplastic anemia, or marked anemia defined as hemoglobin < 10.0 g/dL (or 6.2 mmol/L). 10) Severe cardiovascular disease, defined as any of the following within the preceding 12 weeks: acute myocardial infarction or unstable angina, a coronary revascularization procedure, congestive heart failure (NYHA Class III or IV), or stroke, including a transient ischemic attack. 11) Evidence of cardiac conducting abnormalities, defined as second or third degree AV block not successfully treated with a pacemaker, or a personal or family history of long QT syndrome (QTc interval >450 msec for males or 470 msec for females). 12) End-stage renal disease requiring dialysis. 13) Undergoing transplantation evaluation, or listed with the United Network for Organ Sharing (UNOS) as a lung transplantation candidate at the time of enrollment in this trial. 14) Liver function tests (transaminases, alkaline phosphatase, direct and total bilirubin) >3x upper limit of normal values.
--	--

	
15) Systemically administered potent CYP3A4 inhibitors or inducers are prohibited during the 24-week treatment period.
 
Inhibitors include: boceprevir, cobicistat, conivaptan, ritonavir, itraconazole, ketoconazole, telaprevir, troleandomycin, voriconazole, clarithromycin, diltiazem, idelalisib, nefazodone, nelfinavir.
 
Inducers include carbamazepine, enzalutamide, mitotane, phenytoin, rifampin.
 
See also: https://www.fda.gov/drugs/drug-interactions-labeling/drug-development-and-drug-interactions-table-substrates-inhibitors-and-inducers#table3-2

Study Endpoints:	
 • Primary efficacy endpoint: The primary efficacy endpoint is change in plasma o,o'-dityrosine, as determined by mass spectroscopy, from baseline to Week 24. • Secondary efficacy endpoints: Secondary efficacy endpoints are: (a) collagen degradation products, (e.g., C1M), measured in sera by ELISA; (b) forced vital capacity (FVC); and (c) six-minute walk distance (6MWD) comparing baseline to values at 24 weeks.
	
 • Safety: Adverse events (AEs) that occur anytime during the duration of the trial. Clinical laboratory evaluations will occur at Screening, baseline/Day 1 and Weeks 6, 12, 18, and 24. Urinalysis will be performed at Screening, baseline/Day 1 and Weeks 6, 12, 18, and 24. Pulse rate, SBP and DBP are recorded at Screening, baseline/Day 1 and Weeks 6, 12, 18, and 24. Body weight at Screening, baseline/Day 1 and Weeks 6, 12, 18, and 24. 12-lead ECG at Screening, baseline/Day 1 and Weeks 6, 12, 18, and 24.
	
 • Pharmacokinetics (PK): Plasma concentrations of GKT137831 and its main phase 1 metabolite, GKT138184. The plasma concentrations will be subjected to population PK analysis to estimate population PK parameters such as clearance and volume of distribution and associated inter-individual variability (IIV), and to determine predictors of IIV. PK-PD analysis will be carried out using the primary endpoint and selected secondary endpoints in order to explore any potential PK-PD relationships.

1. OBJECTIVE, SPECIFIC AIMS, BACKGROUND, AND SIGNIFICANCE

1.1 OBJECTIVE

The primary goal of this randomized, multi-center, double-blind, placebo-controlled Phase II clinical trial is to determine the effects of the NOX1/4 inhibitor GKT137831 on plasma levels of *o,o'*-dityrosine, a mechanistic biomarker of pulmonary oxidative stress and injury, among IPF patients. Drug effects on validated clinical endpoints including FVC and 6MWD will be also assessed. We anticipate the findings here will lead to larger incremental trial(s) to determine actual clinical efficacy of this treatment.

1.2 SPECIFIC AIMS

Central Hypothesis: Our primary hypothesis is that treatment of IPF patients with the NOX1/4 inhibitor GKT137831 will reduce pulmonary oxidative injury, as ascertained by reductions in plasma levels of a mechanistic surrogate biomarker (*o,o'*-dityrosine). A corollary of this hypothesis is that treatments that reduce oxidative injury in these patients will have a favorable effect on the natural history of IPF.

The studies proposed here are primarily designed to determine the magnitude of the ROS metabolite reduction and further assess safety of GKT137831 in IPF patients. Nonetheless, we hope that experimental treatments may result in clinically-relevant beneficial effects, as determined by secondary endpoints that include preservation of forced vital capacities and ability to ambulate.

The Specific Aims of this Trial are:

1. To conduct a double-blinded, placebo-controlled Phase II clinical trial in 60 ambulatory IPF subjects at five major medical centers. Subjects will be randomized 1:1 to GKT137831 or matching placebo, and treated for six months. The primary endpoint of this trial will be treatment effects of the experimental drug on plasma levels of *o,o'*-dityrosine, measured by mass spectroscopy pretreatment and at six-week intervals.

*We hypothesize the experimental therapy will reduce plasma levels of *o,o'*-dityrosine, reflecting target engagement of the drug, and reductions of oxidative stress and injury.*

2. To determine the efficacy of GKT137831 therapy in IPF patients, compared to placebo, on four secondary endpoints, measured at baseline and at six-week intervals of: (a) collagen degradation product, C1M, measured in sera by ELISA; and (b) FVC; (c) and 6MWD at baseline and 24 weeks week intervals.

We hypothesize the experimental therapy will decrease circulating levels of C1M. Although the short-duration treatment in this Phase II clinical trial may not result in significant effects on the secondary clinical endpoints, the results of these studies will be critical for the design and power analyses of future GKT137831 Phase III trials. Moreover, this as-of-yet untested drug treatment for IPF may prove to be very effective, and these measures will enable us to detect an unprecedented benefit of this novel approach.

3. To assess the safety and tolerability of GKT137831 in patients with IPF. The incidence and severity of AEs, laboratory tests and ECG abnormalities will be assessed over the course of the trial.

We hypothesize that GKT137831 will have a favorable safety and tolerability profile in IPF patients. There is considerable clinical experience with this compound. To date, over 240 human subjects have been exposed to GKT137831. Completed clinical studies include 4 Phase I studies in healthy subjects, and a Phase II trial in patients with diabetic kidney disease. In addition, GKT137831 is currently being assessed in 2 additional Phase II trials in patients with diabetic kidney disease (DKD) and primary biliary cholangitis (PBC), respectively. To date, no dose limiting toxicity and no safety signals have been identified. There is a major need for effective and well-tolerated therapies for IPF.

This seminal clinical trial could provide evidence that NOX1/4 inhibition is safe and beneficial in IPF patients. Results of this study will help to confirm and establish methods, validate endpoints, and provide the rationale that will facilitate and justify subsequent larger, longer trials to more definitively evaluate the clinical benefits of NOX inhibitors in IPF. *This research has the potential to be paradigm-shifting, will fill several existing gaps, and could ultimately prolong the lives of many patients with this morbid lung disorder.*

The preliminary data that support our central hypothesis are findings from a series of innovative investigations:

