2.2 STUDY DESIGN

Participants will be recruited from among the ambulatory IPF patient populations at the collaborating institutions.

Following completion of screening and eligibility assessments, 60 IPF patients will be randomly assigned to one of two cohorts intended to receive either GKT137831 or matching placebo, in a ratio of 1:1 (i.e., n = 30 in each arm). Both GKT137831 and placebo will be administered by mouth (p.o.), twice daily (b.i.d.). Each GKT137831 capsule will contain 100 mg of the active drug. Drug (and placebo) will be administered for 24 weeks. Each participant will also be surveyed by phone interview at week 28 (one month after completion of drug administration).

All participants will have physiological assessments that are standard of care for IPF patients, including high resolution chest CT scans (HRCT scans), and pulmonary function tests (spirometry, diffusion capacity, 6-minute walk distance) prior to and after the conclusion of therapy. These procedures and routine laboratory tests will not be repeated specifically for this study if they are deemed to be clinically indicated. The results of any standard-of-care procedures will be extracted from the participant's medical record and used as research data.

Patients will be monitored carefully for occurrences of adverse events. Adverse experiences will be evaluated according to criteria outlined in the NCI Common Terminology Criteria for Adverse Events (CTCAE), version 5.0.

Patients removed from treatment due to unacceptable adverse events will be followed for a total of 24 weeks under the principle of intent to treat.

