2.6.5 Specimen Collection and Management

Specimen Collection / Documentation: A maximum of 34 ml of blood for experimental research studies and endpoint assays will be obtained pretreatment, and at weeks 6, 12, 18, and 24 after the start of therapy. The peripheral blood will be processed at the site of collection by centrifugation to separate mononuclear cells, plasma, and sera, which will be aliquoted and frozen (at -20° or below) until shipment to the CCC in batches. Subsequent assays will be conducted in the laboratory of CCC investigators or their colleagues, in compliance with IRB approvals.

Each research sample will be labeled with the subject's unique identifier, sample date, and sample collection time. The code number and date on which the specimen is frozen, all other information about the specimen, and subsequent processing will be entered on a specimen processing worksheet.

Covariate information, e.g., concomitant medications, laboratory values, etc., will be obtained at each time point.

Specimen Handling and Labeling (De-Identification)

All research specimens and all records associated with the samples will be labeled only with a unique code that links to the trial data, but contains no personal identifiers. The information linking these code numbers to the corresponding subject's identity will be kept in a secure location in the PI's office at each participating center, and will not be available to staff managing samples at the research laboratories.

Specimen Management and Storage: Specimens in excess of immediate assay requirements may be stored indefinitely in a secured freezer under the control of the responsible PI. The coding information linking patient identifiers to the stored samples will be maintained in a locked, secure area that will be accessible only to the study investigator. Subjects may request to have their samples destroyed at any time. These samples will be destroyed immediately upon receipt of the subjects' written request to do so.

Restrictions to Direct Access of Specimens: Specimens will be kept in the responsible study investigators' laboratories indefinitely and will be under the control of the PI. Other personnel not involved with the management or operations of the study are not permitted direct access to the specimens.

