2.8 DATA ANALYSES AND POWER ANALYSES

2.8.1. Data analyses: Baseline demographic and clinical data of participants will be summarized using means (with standard deviations) and medians (with inter-quartile ranges) for continuous variables, and counts and percentages for discrete variables, stratified by treatment group. Differences between groups (to examine the randomization effectiveness), will be assessed by t-tests, or by Fisher's exact test for discrete data. Analyses will follow intention to treat principles, with the last observed outcome over all time points being used as the primary measure for a given variable. Multiple imputation will be used based on subject characteristics to assess the obvious issues, with last observations carried forward in these analyses. Trajectories over time, for a given patient and outcome measure, will be displayed via line graphs, and assessments conducted using generalized linear models on the repeated time points. Comparisons between the treatment arms of circulating o,o'-dityrosine levels at various time points will be made using these repeated measures techniques. Transformations of these tests may be needed, such as velocities, if many individuals are unable to complete the entire protocol.

2.8.2. Power analyses: The sample size of 60 for this clinical trial (equally divided between experimental and placebo arms) is based on exposing a minimum number of patients to risks of experimental therapy, while still obtaining useful information. We previously found that o,o'-dityrosine levels ($\mu\text{mol/mol}$ tyrosine) in IPF patients ($n = 32$) were 8.51, with a standard deviation (SD) of 5.30, compared to mean and SD of 0.47 ± 0.45 in normal controls (15). Assuming o,o'-dityrosine levels are reduced in the experimental arm subjects by 50% of the difference between untreated IPF and normals (e.g., to $4.02 \mu\text{mol/mol}$ tyrosine), with a SD of 5.3 we will be able to reject the null hypothesis that the population means of the experimental and control groups are equal with probability (power) 0.82, using an unpaired, two-way t-test. The Type I error probability associated with this test of this null hypothesis is 0.05. The 50% reduction is well within ranges in which ROS and fibrosis markers are decreased by GKT137831 in other models (Sec. 1.3.9., and 8-11).

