As an example of other factors, IPF patients who are already listed for lung transplantation will be excluded from participation. Participants will **not be prohibited from transplantation** at any time

during or after participation in this trial, since we cannot ethically preclude lung transplants (considered a definitive treatment) to a subject in this trial who, for whatever reasons, might become transplant eligible. Exclusions of subjects already listed with UNOS or those whose listing may be eminent will minimize very early drop-outs due to transplantations, and preclude any potential concerns about performing these procedures in patients currently treated with a NOX inhibitor. Notwithstanding, most ambulatory IPF in our centers are transplant ineligible due to age or co-morbidities.

Frequent outpatient visits are already routine standard of care for IPF patient care, and study compliance of these patients is typically very good (and probably better than in most other, less lethal, disease populations). As examples, study procedures were completed in 39/44 (88%) of the UAB patients entered into ACE-IPF, STEP-IPF, or PANTHER-IPF (durations of 48, 12, and 60 weeks, respectively). None of the 30 subjects enrolled in ART-IPF (including the 19 at UAB and Temple) have been lost to follow-up due to noncompliance during their 9 month trial observations. As in ART-IPF, participants will be compensated for routine travel expenses, as needed. Adherence to the treatment regime will be assessed at each outpatient visit using a combination of pill counts, reviews of patient diary data, and verbal reviews of medications taken. Assessments of adherence, and encouragement (reinforcement) for same, will also occur during phone contacts that occur at 2 week intervals in between face-to-face outpatient visits.

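### The last-observed rule for dityrosine uses an off-drug value for an active-arm patient who stops and attends Week 24, but an earlier value for one who stops and leaves, so the contrast depends partly on attendance

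*Combined protocol and SAP*

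**What the plan says.** Section 1.2 states the primary hypothesis as a reduction in pulmonary oxidative injury, shown by lower plasma dityrosine. Under Aim 1 it interprets that reduction as "reflecting target engagement of the drug, and reductions of oxidative stress and injury". The synopsis (Study Endpoints) defines the primary endpoint as change in dityrosine, "as determined by mass spectroscopy, from baseline to Week 24". Under section 2.6.5, blood is "obtained pretreatment, and at weeks 6, 12, 18, and 24 after the start of therapy".

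Section 2.2 says that patients removed from treatment for unacceptable adverse events "will be followed for a total of 24 weeks under the principle of intent to treat". Section 5.6.1 lists several reasons for stopping drug, including the patient's request to withdraw. It does not say whether sampling continues after a stop for other reasons.

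Section 2.8.1 specifies intention-to-treat analysis, "with the last observed outcome over all time points being used as the primary measure for a given variable". It continues: "Multiple imputation will be used based on subject characteristics to assess the obvious issues, with last observations carried forward in these analyses". It also describes "assessments conducted using generalized linear models on the repeated time points" and assigns the between-arm dityrosine comparisons at the various time points to these repeated-measures methods.

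Section 4.1.2 assesses adherence at each outpatient visit by a "combination of pill counts, reviews of patient diary data, and verbal reviews of medications taken". No analysis is described that uses those adherence data. Sections 2.7.4 and 2.8.4 provide for drug and metabolite concentrations at Weeks 6 and 12 and an exploratory PK-PD analysis of the primary endpoint.

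**The concern.** Target engagement by an enzyme inhibitor exists only while drug is present. Under the last-observed rule, two active-arm patients who stop on the same day for the same reason can enter the primary comparison with different kinds of value. One stays for visits and is represented by a Week 24 sample taken off drug. The other leaves and is represented by an earlier sample, perhaps taken on drug. Only attendance differs between them. In the placebo arm the distinction has no pharmacological meaning, so it does not cancel between arms.

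If dityrosine rises again after stopping, better retention of stoppers gives a smaller estimated effect for the same pharmacology. Nothing in section 2.8.1 says how samples drawn after stopping are treated. A small or null difference would then be harder to interpret in a proof-of-concept trial whose results are meant to inform the design of a Phase III study.

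**Working it through.** **1. What each type of active-arm patient contributes under the last-observed rule**

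| Active-arm patient | Value used |
|---|---|
| Stays on drug to Week 24 | Week 24, on drug |
| Stops, attends Week 24 | Week 24, off drug |
| Stops and leaves after an on-drug sample | That earlier sample, on drug |
| Leaves before the Week 6 sample | Baseline, i.e. zero change |

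An intention-to-treat effect at Week 24 would need a Week 24 value, observed or modelled, in every row. An on-drug effect would exclude the off-drug value in row 2. The rule does neither.

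**2. The plan's own power figure**

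Inputs from section 2.8.2: means 8.51 (IPF) and 0.47 (controls), a reduction of 50% of the gap, SD 5.3, 30 per arm, two-sided alpha 0.05 (its two-way t-test read as two-sided).

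- Difference: 0.5 × (8.51 − 0.47) = 4.02.
- Standardised difference: 4.02 / 5.3 = 0.758.
- Noncentral-t power: 0.823. The stated 0.82 is reproduced.

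**3. How far attendance can move the result**

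Let *d* be the share of the active arm that stops drug, *a* the share of stoppers who still attend Week 24, and *r* the share of the effect lost off drug. Leavers are taken to have left after an on-drug sample that shows the full effect. Then:

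expected difference = 4.02 × (1 − *d* × *a* × *r*)

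If all stoppers leave (*a* = 0), the difference stays at 4.02 and power at 0.82. If all attend (*a* = 1):

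| *d* | Full loss (*r* = 1): difference, power | Half loss (*r* = 0.5): difference, power |
|---|---|---|
| 1/68 | 4.02 × (1 − 1/68) = 3.96, 0.81 | not needed |
| 7% | 4.02 × 0.93 = 3.74, 0.77 | 4.02 × 0.965 = 3.88, 0.80 |
| 12% | 4.02 × 0.88 = 3.54, 0.72 | 4.02 × 0.94 = 3.78, 0.78 (0.775) |
| 20% | 4.02 × 0.80 = 3.22, 0.64 | 4.02 × 0.90 = 3.62, 0.74 |

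Only the product *a* × *r* matters, so the half-loss column also describes full loss with half of the stoppers retained.

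**4. Where the stopping rates come from**

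All are assumptions for this trial.

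- 1/68 is the active-arm rate of discontinuation for safety events in the diabetic kidney trial (section 5.1.2): 12 weeks, lower doses, another disease.
- 7% is the complement of the 93% who completed treatment in the 24-week PBC trial (section 1.3.12).
- 12% is rounded from 5/44 = 11.4%, the patients at one site who did not complete study procedures in earlier IPF trials of 12 to 60 weeks (section 4.1.2). It measures incomplete study procedures, not patients who stopped drug and kept attending.
- 20% has no source in the documents.

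**The case against.** Several points on the other side are sound.

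- **The hypothesis.** A reader might infer that the primary hypothesis is target engagement and that off-drug values therefore have no place in the primary contrast. Section 1.2 does not support this. Its primary hypothesis is reduced oxidative injury, and engagement is one part of Aim 1's interpretation. For an injury hypothesis, a Week 24 comparison that includes off-drug time is legitimate.
- **A null result.** A reader might infer that a null result could never be separated into no engagement and drug not taken. The PK-PD analysis addresses part of that question, since it relates measured exposure to dityrosine. It is exploratory and has no samples at Week 18 or 24, so it helps but does not close the gap.
- **The analysis text.** Section 2.8.1 also names multiple imputation and repeated-measures models, so it does not settle on a single rule. However, the last observed value is what it calls the primary measure, and neither alternative is tied to drug discontinuation.
- **The size.** Off-drug follow-up is explicit only for adverse-event removals. Section 1.3.7 describes the oxidative modifications as stable, and no rebound rate is given, so full loss may be too pessimistic. At 1/68 the effect on power is about one point. Anyone who leaves before Week 6 contributes baseline, so leaving does not always preserve the on-drug effect.

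These points limit the size and the wording. They do not remove the dependence on attendance.

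**Conclusion.** The concern holds. As written, section 2.8.1 combined with the follow-up in section 2.2 gives a dityrosine contrast that is neither an intention-to-treat effect at Week 24 nor an on-drug effect, and that shifts with how many stoppers keep attending.

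The size cannot be fixed from the documents. Across the assumed rates in the table, power with all stoppers retained lies between 0.81 (1/68, full loss) and 0.64 (20%, full loss), against 0.82 if none is retained. These figures assume an unaffected placebo arm, SD unchanged at 5.3, all 30 per arm analysed, and leavers who had shown the full effect. They compare the extremes of retention and should not be read as a forecast of power for this trial.

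The lack of an on-drug contrast is not an error in itself. The defect is the last-observed rule, together with the lack of any statement on samples drawn after stopping. It should be corrected before unblinding.

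**What to change.** Change section 2.8.1 in two places.

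1. **Primary contrast.** For dityrosine, replace the last-observed and carried-forward rule with the Week 24 treatment contrast from the repeated-measures model already named. Use every sample collected, whether or not drug had been stopped. Handle missing Week 24 values through that model or by multiple imputation, and do not carry values forward. Without a rule for patients who have no Week 24 sample, the primary contrast would still depend on attendance.
2. **Supportive contrast.** Pre-specify one further contrast from the same model, with samples drawn after stopping drug (by diary and pill count) set to missing under the same rule in both arms. Report it beside the exploratory PK-PD analysis when interpreting target engagement.

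The cost is a few lines of text and an on-drug flag derived from adherence data already collected. No new visits or samples are needed. The downside is that the second contrast is not fully protected by randomisation, because stopping drug may be related to outcome, so it must be labelled supportive.
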